We hypothesize that high levels of IN-OT will enhance brain activity and functional connectivity of social brain networks areas involved in perception and emotional processes in response to dynamic social cues as compared to non-social cues. We are also interested in looking into the effects of IN-OT on reducing the activity of amygdala and anterior hippocampus in a context dependent fashion (as based on level of stress). We also believe that the clinical/behavioral and endophenotypes will play a fundamental role in determining OXT's effects on brain activity.

Primary outcome measure: Here, we are looking to differences between treatments conditions on BOLD activity of perceptual and emotional brain regions while participants play a multi-player ball game. We predict that a higher dose of IN-OT will enhance the BOLD activity of reward brain regions (such as OFC, ventral striatum, Nucleus accumbens, ventral tegmental area) and perceptual brain regions (such as inferior occipital, fusiform gyrus, superior temporal sulcus, amygdala, superior parietal lobe) and insight awareness (insula and ACC) for facial expressions as compare to neutral non-social trials, *regions that are expected to be less activated in placebo as compared to healthy subjects*. We also expect increased activity in rewarding brain regions in response to positive social feedback as compared to neutral social feedback. We also expect to find a main effect of IN-OT on reducing the activity of amygdala and hippocampus during the ball-game, in a context dependent manner (which could be related to a reduction of stress and anxiety). Indeed, we expect to find the neutral feedback trials to be more stressful and activating more the amygdala when compared to the positive trials.

Indeed, in contrast to positive feedback, we expect the neutral to be eliciting negative social feedback in this kind of social context.

Secondary outcome measure:

We are looking into differences between treatment conditions on behavioral outcome of social learning paradigm (post scanner) following the ball-game. We are looking into implicit effects of learned emotional associations on reaction time. We expect to find more emotional implicit social biases with IN-OT.

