**For aim 3:** *The primary outcome measure* of the third outcome measure consist of studying the different effects of treatments on BOLD activity of key brain regions (OFC, ventral striatum, inferior occipital cortex, fusiform gyrus, amygdala, superior parietal lobe, insula and ACC) while playing a social interactive ball-game in ASD. During this ball-game, we will analyze the BOLD brain activity during social output videos that will display either neutral or positive face expressions. We expect more rewarding brain regions to be more activated during the process of positive social feedback with oxytocin treatment. In order to determine TEE-OXT, we will conduct repeated ANOVA analysis with variables (BOLD activity in response to positive and neutral) and treatments (8, 24, 48, placebo). We will also investigate the general effect of TEE-OXT on the BOLD activity of socio-emotional brain regions in response to both positive and neutral faces with the variable (BOLD activity in response to all faces) and treatments. We will also investigate the differences between oxytocin treatment and placebo. We expect at least the doses of 24IU and 48IU to be different from placebo. Covariates such as visit order will be entered in the GLM model as a regressor to control for habituation effects.

*The secondary outcome measure* consists of studying the effects of treatments on behavioral outcome measure (post scanner on social learning). In this behavioral task, we will analyze the accuracy and reaction time in recognizing faces as familiar. We will conduct ANOVA and t-tests to compare the performance in these 2 variables (accuracy and reaction time) between the 4 treatment conditions.

**For aim 4:** *The primary outcome measure* of the fourth outcome measure consists of investigating the differences between treatments on the modulation of brain activity of reward brain regions in response to punishment and helpful behavior. In the GLM model, we will conduct an ANOVA or t-tests with 4 treatment conditions and the BOLD signal in NAcc, OFC, VTA and ACC.

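### Aim 3's lead prediction, faces against non-social trials, has no matching analysis in the statistical section

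*Combined protocol and SAP*

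**What the plan says.** Objectives, Aim 3, opens with the hypothesis that high levels of oxytocin will enhance activity and connectivity "in response to dynamic social cues as compared to non-social cues". The primary outcome repeats this as a prediction for reward, perceptual and awareness regions: a higher dose will raise activity "for facial expressions as compare to neutral non-social trials". Two further predictions follow. One concerns valence: "We also expect increased activity in rewarding brain regions in response to positive social feedback as compared to neutral social feedback". The other is a "main effect of IN-OT on reducing the activity of amygdala and hippocampus during the ball-game".

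The Aim 3 paragraph of Statistical analysis says that activity will be analysed during "social output videos that will display either neutral or positive face expressions". It then lists three analyses:

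- a "repeated ANOVA analysis with variables (BOLD activity in response to positive and neutral) and treatments (8, 24, 48, placebo");
- a general effect "with the variable (BOLD activity in response to all faces) and treatments";
- a drug comparison: "We will also investigate the differences between oxytocin treatment and placebo".

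Visit order enters the model as a regressor. The paragraph names no non-social trial, condition or contrast.

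**The concern.** The hypothesis is about social specificity: oxytocin should act on the response to social cues more than on the response to non-social ones. Testing that needs a non-social reference in the model, and the analysis paragraph has none.

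What is at stake is interpretation. If all-faces activity rises with dose, the rise could reflect social processing. It could equally reflect a drug effect on the BOLD response in general, on arousal or on attention. A report that read such a result as confirming the Aim 3 hypothesis would claim more than the analysis can show.

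**Working it through.** The point rests on text. The plan gives no figure for this contrast, so there is none to reproduce. The inputs are the predictions in Objectives, Aim 3, and the analyses in the Aim 3 paragraph of Statistical analysis.

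**Step 1: pair predictions with analyses.**

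1. Faces above non-social trials at a higher dose: no analysis named.
2. Positive above neutral feedback in reward regions: covered by the positive/neutral by treatment ANOVA.
3. Lower amygdala and hippocampal activity during the game: the all-faces by treatment analysis is closest. The amygdala is on the Aim 3 region list in Statistical analysis; the hippocampus is not.

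**Step 2: check whether the missing contrast can be recovered.** Order the responses as (positive face, neutral face, non-social trial). The weights are:

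- positive minus neutral: (1, −1, 0)
- all faces: (0.5, 0.5, 0)
- all faces minus non-social: (0.5, 0.5, −1)

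Any combination a·(1, −1, 0) + b·(0.5, 0.5, 0) equals (a + 0.5b, −a + 0.5b, 0). Its third entry is 0 whatever a and b are, and the lead prediction needs −1. The two planned contrasts have rank 2, and adding the third gives rank 3. The lead contrast is therefore not a combination of the planned ones. The oxytocin against placebo comparison states no stimulus contrast, so it adds no non-social weight.

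**Step 3: what each contrast would show.** Suppose a dose changes the response to faces by s + g and the response to non-social trials by g, where s is social-specific and g is common to both.

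- All faces: s + g. This is non-zero when s = 0 and g ≠ 0.
- Faces minus non-social: (s + g) − g = s.
- Positive minus neutral: (s_pos + g) − (s_neu + g) = s_pos − s_neu. This is a valence effect within social cues. The Objectives expect neutral feedback to act as negative social feedback, so it is not a non-social reference.

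The cancellation holds only for an additive effect common to both trial types. If the drug multiplies responses F (faces) and N (non-social) by k, the difference changes by (k − 1)(F − N), which is zero only when F = N.

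**Step 4: look elsewhere in the document.** The only other mention of social against non-social in Statistical analysis is in the power sentence for healthy subjects. They receive placebo only, so that comparison cannot test an oxytocin effect in ASD. The exploratory analyses compare ASD with controls. The closing paragraph leaves further detail to later amendments and names no contrast.

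**The case against.** Several counter-arguments have force.

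- **Aim 3 is not left empty.** The valence prediction is tested, and the amygdala main effect is reasonably served. A reader might infer that the trial cannot answer Aim 3, or that one of only two primary contrasts is missing. The Objectives list at least three predictions, and only the lead one lacks an analysis.
- **The all-faces analysis has its own purpose.** A reader might infer that faces minus non-social should replace it. That would remove the test closest to the predicted amygdala reduction: a reduction common to both trial types would cancel in the difference.
- **Drift between visits is largely handled.** Treatment is assigned at random across visits within each patient, and visit order is a covariate. What remains is a non-specific effect of the drug itself.
- **Face responses may be estimated against an implicit baseline.** That would already remove much of a simple shift in signal level. The plan does not say so, and such a baseline is not the non-social control named in the Objectives. Nor would it remove a drug effect on the response itself, on arousal or on attention.
- **Non-social trials may not exist in usable form.** The task descriptions under the second visit do not mention them. Their existence is implied by the Objectives and by the healthy-subject power sentence, but their number and timing are not given. This stands, and it makes the fix conditional.
- **Detail is deferred to amendments.** The gap may therefore be an omission and not a deliberate choice, but the deferral does not supply the contrast.

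**Conclusion.** The concern holds in a limited form. Aim 3's lead prediction has no matching analysis, and it cannot be reconstructed from the analyses that are planned. An all-faces effect by itself does not support a social-specific conclusion.

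The size is one untested prediction out of at least three in the Aim 3 primary outcome. The documents give no basis for putting a number on a non-specific drug effect. A reader might infer that any such effect passes in full into the all-faces result and disappears from the difference. The documents do not support that: it depends on the unstated baseline and on the effect being additive and equal across trial types.

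The conclusion assumes that the Aim 3 paragraph lists all the planned Aim 3 task contrasts. It does not assume that non-social trials were scanned. With or without them, the hypothesis and the analysis must be reconciled.

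**What to change.** In the Aim 3 paragraph of Statistical analysis, add the contrast treatment by (all faces minus non-social trials), with visit order as covariate, and name it as the first Aim 3 primary contrast. Keep positive against neutral by treatment. Keep all faces by treatment for the predicted amygdala main effect.

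First confirm from the task design that the ball game as scanned contains usable non-social trials, and describe them in the protocol. If it does not, restate the hypothesis and the first prediction in Objectives, Aim 3, to match the analysis, and draw no social-specific conclusion.

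The blind is to be broken at 25 patients for a mid-way analysis of primary outcomes, and the healthy-subject screening section says patient testing is already complete. The amendment should therefore state which data had been unblinded when the contrast was added.

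If the trials exist, the cost is one further contrast in the existing model. There are two downsides: one more contrast enters whatever multiplicity correction is applied to Aim 3, and a difference between conditions is usually noisier than all faces alone.

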## **ASD subjects**

Upon arrival, staff will review the screening form previously filled as well as eligibility criteria and the MRI screening form out for correctness and affirm that no changes in their health or medical history have occurred. If any changes have occurred, the study staff will consult with the PI or the study physician, if necessary. We will review the consent form with the subject. We will also assess his understanding of the consent by asking specific questions that are part of an assessment of capacity form. The experimenter will ask the questions to the patient and will take notes of his responses. If the patient did not answer correctly to all questions, we will review the consent again and ask the questions again to ensure a full understanding of the consent. Once the patient understands the consent, we will proceed to the signature. This assessment of capacity form will be only administered to patients with ASD and not to healthy subjects.

The nurse practitioner or the study physician will conduct a brief history and physical. The nurse practitioner will go through the inclusion and exclusion criteria again to ensure that the patient is ready to participate in the subsequent clinical visit. This health assessment will be reviewed again one more time during one of the subsequent clinical visits.

Participants will fill a family history form related to themselves and to their family history .

We will collect saliva samples (3 DNA Genotek kits) for genotyping analysis and methylation analysis.

The patient will complete several questionnaires.

Given that there is lot of questionnaires to complete, we can ask participants if they prefer to complete them at home. Participants can complete the questionnaires and bring them back during the following visits.

Participants will also perform a social learning test during which the participants match faces or words as fast as possible. This test is an adaptation of the implicit association task during which we study implicit associations.

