  - **Face Rating questionnaire (post MRI):** participants are asked to rate (on a scale 1 to 7) faces.
  - **A social learning test (SLT):** participants are asked to match faces and words as fast as they can.
  - **Emotion Matching test (EMT):** participants are asked to identify the emotion that is displayed on a face by matching the emotional face that appears on the left to one of the faces that appears to the right (different faces but same emotion).
  - **Toronto Alexithymia scale:** participants are asked to complete a simple questionnaire.
  - **Mood questionnaire (PANAS scale).**
  - **BB-CGI (clinical interview):** the same interview that is performed during the pre-MRI visit will be performed during this visit in order to collect a clinical score of improvement as well as physiological, verbal and socio-emotional improvements.

4- Second, Third and Fourth visit of scan (ASD subjects) (total duration= around 3 to 4 hours each): The exact same procedures will be performed during these other 3 visits. These 3 additional visits will be conducted only in ASD subjects. Also, participants will receive different content of spray (either different dose of oxytocin or placebo).

Of note, the health assessment will be reviewed one more time (in addition to the assessment during the first pre-clinical visit) by the nurse practitioner or the study physician during one of the 4 clinical visits, if the original health assessment expires (more than 30 days).

	Screening and consent review/training	Vital signs 1	Blood samples Pre	Hormone Spray (PL, 8, 24, 48 IN-OT)	Blood samples post	Vital signs 2	MRI scan	Post MRI scan
Visit 1	X	X	X	X	X	X	Rest+ 3 tasks	Quest+ 2 tasks + clinical interview
Visit 2	X	X	X	X	X	X	Rest+ 3 tasks	Quest+ 2 tasks + clinical interview
Visit 3	X	X	X	X	X	X	Rest+ 3 tasks	Quest+ 2 tasks + clinical interview
Visit 4	X	X	X	X	X	X	Rest+ 3 tasks	Quest+ 2 tasks + clinical interview

Table 2: Clinical trial visits for subjects with ASD

Visits will be separated by a one-week interval approximately ( $\pm$  2 to 3 days). We have to be flexible with the scheduling given that we are facing challenges while scheduling all the units and personals. Every patient will receive the 3 doses of IN-OT (8IU, 24IU, 48IU) and placebo in a double blind, placebo controlled trial.

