Withdrawals, missing data and ineligible patients will be stated. Data will be controlled and double checked by the PI before publishing papers. Outliers will be investigated with statistical tools. Post-analysis will be checked for quality and checked for confounder factors, covariates. Additional precision on the type of analysis (behavioral, physiological and brain) will be submitted as amendments once the PI and staff members start working on the analysis of the data of the project.

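### The Aim 3 secondary analysis compares familiarity accuracy and reaction time across treatments, with no association or emotion factor, so as written it does not test the stated implicit-bias hypothesis

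*Combined protocol and SAP*

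**What the plan says.** **Objectives, Aim 3, secondary outcome measure.** The outcome is "differences between treatment conditions on behavioral outcome of social learning paradigm (post scanner) following the ball-game". The variable is then given: "We are looking into implicit effects of learned emotional associations on reaction time". The prediction is directional: "We expect to find more emotional implicit social biases with IN-OT".

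**Task descriptions.** Under the pre-clinical visit for ASD subjects, the social learning test is introduced with the words "This test is an adaptation of the implicit association task during which we study implicit associations". In the list of post-MRI tasks for the first scan visit, "participants are asked to match faces and words as fast as they can". Neither place mentions judging whether a face is familiar.

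**Statistical analysis, aim 3, secondary outcome.** For the same post-scanner test, "we will analyze the accuracy and reaction time in recognizing faces as familiar". The planned test follows: "We will conduct ANOVA and t-tests to compare the performance in these 2 variables (accuracy and reaction time) between the 4 treatment conditions".

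**Close of the Statistical analysis section.** "Additional precision on the type of analysis (behavioral, physiological and brain) will be submitted as amendments", with the timing set at the point when the team begins to analyse the data.

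**The concern.** The objective and the analysis name the same test but not the same quantity. The objective concerns a bias, which is a contrast between kinds of trial within one session. The analysis concerns how accurately and how fast faces are judged familiar, compared between treatments only. A patient could become faster overall with no change in bias, or show a changed bias with no change in overall speed.

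If the plan is followed as written, the trial would report on its oxytocin bias prediction with numbers that do not bear on it. A second risk is that two descriptions of one outcome leave the choice between them open. The Healthy subjects screening section says that testing of the ASD group is complete, and analysis detail is deferred until data analysis starts. The choice could therefore be made with data in hand.

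**Working it through.** No figure in the plan is at issue, so the check compares the texts and then asks what the planned comparison can detect.

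**1. The two definitions side by side**

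| Element | Objectives, Aim 3 | Statistical analysis, aim 3 |
|---|---|---|
| Test | Social learning test, after the scan | Social learning test, after the scan |
| Variable | Reaction time, as a sign of implicit associations | Reaction time and accuracy in familiarity judgements |
| Condition within the test | Learned emotional associations | None named |
| Prediction | More bias with oxytocin | None stated |
| Comparison | Between treatments | Between four treatments, ANOVA and t-tests |

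Test, reaction time and treatment comparison agree. Accuracy and the familiarity judgement appear only in the analysis. The associative condition appears only in the objective. No other part of the document analyses implicit bias, and none describes a familiarity judgement within this test.

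**2. What the planned comparison can detect**

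Let Y1 and Y2 be a patient's mean reaction times under one treatment in two association conditions, equally weighted.

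- Bias: D = Y1 − Y2.
- Reaction time with no condition factor: M = (Y1 + Y2)/2.

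Suppose oxytocin changes both conditions by t. Then M changes by t, and D changes by (Y1 + t) − (Y2 + t) − (Y1 − Y2) = 0. The planned test would see an effect although there is no change in bias.

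Suppose instead that oxytocin changes the bias by d, as +d/2 in one condition and −d/2 in the other. Then D changes by d, and M changes by (d/2 − d/2)/2 = 0. The planned test would see nothing although the hypothesis is true.

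The hypothesis therefore concerns the treatment-by-condition effect. The planned comparison is a treatment main effect. Accuracy does not enter the hypothesis at all.

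**3. Does the plan name a condition factor elsewhere?**

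Yes. The Aim 3 primary analysis crosses positive and neutral faces with treatment and enters visit order in the GLM. The secondary analysis names neither the factor nor the covariate.

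**4. Repeated testing**

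ASD patients take the test at the pre-clinical visit and after each of four scans, so up to 1 + 4 = 5 times. If practice shortens every reaction time by the same amount s, then (Y1 − s) − (Y2 − s) = Y1 − Y2, and D is unaffected. If practice multiplies every reaction time by a factor k, then kY1 − kY2 = k(Y1 − Y2), and D shrinks with M. The difference score removes session-wide speeding fully only in the additive case.

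**The case against.** The best defence is that the analysis paragraph is short rather than wrong. It keeps reaction time on the same test, and ANOVA does not rule out a within-task factor. The familiarity judgement might even be the response in which the bias shows: faces met in the ball game with positive or neutral feedback could later be recognised at different speeds. The task descriptions are single lines with no trial structure, so this reading cannot be excluded. It is fair to say that reaction time is retained, and a reader who infers that the stated outcome has been replaced by two unrelated ones goes further than the text allows. Even on this favourable reading, however, the contrast that would carry the bias is still missing from the analysis.

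A second defence is the promise of later amendments. A reader might infer from the present text that the hypothesis will never be tested. The documents do not show that, since the plan presents its behavioural analyses as open to further detail. But a promise tied to the start of data analysis does not repair a comparison that already differs from its outcome.

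Third, a reader might infer that practice over repeated sessions biases the raw reaction-time comparison. The Aim 2 analysis describes treatment order as fully randomised, so practice should mainly add variance, and systematic bias is limited.

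Fourth, a reader might link this outcome to the planned unblinding at 25 ASD patients. The Statistical analysis section aims that look mainly at brain measures and at primary outcomes, so this test is not its target. The freedom to choose a definition remains for the final analysis.

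**Conclusion.** The point stands: as written, the Aim 3 secondary analysis does not test the Aim 3 secondary hypothesis. This is a mismatch between outcome and analysis, and more than missing detail, because the specified comparison could be carried out in full and still leave the prediction unanswered. It affects one behavioural secondary outcome with a directional prediction, the only secondary outcome that Aim 3 has. It should be corrected, but it does not threaten the trial's primary aims.

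The conclusion rests on two readings: that a bias means a within-person difference between conditions, as the implicit-association description implies, and that an analysis naming only treatments has no further factor. It does not rest on any particular task design. A reader might infer from the implicit-association label that the test contains congruent and incongruent face-word pairings. No part of the document says so, and the contrast nearest to the objective may be faces with positive versus neutral learned associations.

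**What to change.** In the aim 3 secondary paragraph of the Statistical analysis section:

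1. Define the outcome as the within-session reaction-time difference between the association conditions that the task contains. Candidates are faces with positive versus neutral learned associations, or the pairing types of the adapted implicit association task. Confirm which against the task design, and state how reaction times are scored.
2. Test it as a treatment-by-condition effect within patients, with visit order in the model. This matches what the Aim 3 primary analysis already does with face type.
3. Label familiarity accuracy and raw reaction time as exploratory.
4. If the task records no such conditions, restate the Aim 3 secondary outcome and hypothesis in the Objectives as familiarity recognition, describe that judgement in the procedures, and drop the implicit-bias claim.

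Make the change before any further unblinded analysis of this test.

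The cost is wording, plus a derived score if trials are logged by condition, which the documents do not establish. The statistical price is noise. With n trials split equally and trial-level error variance σ², each condition mean has variance 2σ²/n, so their difference has 4σ²/n, against σ²/n for the overall mean. Variation shared by the whole session is removed from the difference, fully so only if it is additive, which offsets some of this.
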